Rescreening may be allowed for subjects who failed initial screening. Only 1 rescreening will be allowed (see [Section 5.1](#) and [Section 5.2](#)). If a subject is rescreened for the study, the subject must sign a new informed consent and will be issued a new subject number. Informed consent for a rescreened subject must be obtained prior to performing any study-related assessments or collecting any data for the Screening visit.

Treatment period

On Day 1, eligible subjects will enter an open-label treatment period to receive ligelizumab 120 mg sc q4w. The first dose of study drug will be administered on Day 1 (Visit 110). The last dose of ligelizumab 120 mg will be administered on Day 337 (Week 48, Visit 230) study visit.

Approximately 65 subjects will be allocated to the ligelizumab 120 mg q4w arm. Subjects are expected to attend all site visits based on the assessment schedule ([Table 8-1](#)).

Post-treatment follow-up period

The post-treatment follow-up period is 12 weeks with the last follow-up visit (Visit 1999) corresponding to 16 weeks after the last treatment dose. No investigational treatment will be given during the post-treatment follow-up period. Subjects will be allowed to take their rescue medication on an as needed basis, assessed on a daily basis by the subjects. Subjects will be required to visit the study center every 4 weeks during the post-treatment follow-up period.

Patients will be eligible for post-trial access after completion of the study.

4 Rationale

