4.5 Risks and benefits

In the overall ligelizumab clinical program, approximately 900 subjects have been exposed across 12 studies, covering the indications of CSU, asthma, atopic dermatitis, and bullous pemphigoid (BP). The longest individual continuous exposure to ligelizumab is 12 months ([CQGE031C2201E1] and [CQGE031B2201E1]). Cumulative (continuous and interrupted) human duration of exposure to ligelizumab is approximately 16 and 17 months (across the [CQGE031B2201]/CQGE031B2201E1 asthma studies and the [CQGE031C2201]/CQGE031C2201E1 CSU studies, respectively). The following doses have been tested in the clinical programs: 12 mg, 24 mg, 36 mg, 72 mg, 180 mg and 240 mg sc q4w, 280 mg q2w and 120 mg sc single dose. To date in the CSU program alone, 254 subjects have been exposed to ligelizumab at doses up to 240 mg sc q4w.

Overall, no apparent dose-dependent safety signals (except for a trend in injection site reactions, which can be easily managed clinically) have been observed to date, although the number of subjects studied is relatively small, in line with the development phase of the CSU program. In the clinical study CQGE031B2201 in the patients with asthma, there appeared to be a dose dependency of injection site reactions between ligelizumab high dose group (28.6% of 199 subjects) and ligelizumab low dose group (12.5% of 40 subjects), which was comparable to omalizumab (14.5% of 131 subjects). The incidence of injection site reactions was higher among all the active treatment groups compared to that of placebo (5.2% of 96 subjects). Similarly, in the CSU dose-finding study (CQGE031C2201), the overall safety profile was comparable between different doses of ligelizumab (24 mg, 72 mg and 240 mg q4w or 120 mg

single dose), omalizumab and placebo. In both studies (CQGE031B2201 and CQGE031C2201), the patients on the higher doses of 180 mg and 240 mg had 2 injections with active in contrast to the patients on lower doses of 12 mg, 36 mg, 72 mg and 120 mg who received one active and one placebo injection. The exceptions were AEs related to injection site reactions, where a possible trend of dose dependency for ligelizumab was observed. All cases of injection site reactions (except 1 case of medical significance) regardless of treatment group or doses were non-serious, mild to moderate in severity, reversible, and did not lead to discontinuation of study treatment.

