6.1.3 Treatment arms/group

All eligible subjects will be assigned at Visit 110 to ligelizumab group. Each subject will receive 1 injection of 1.0 mL ligelizumab every 4 weeks.

During the treatment period, study drug will be administered for 13 visits as per [Table 8-1](#).

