6.6 Additional treatment guidance

6.6.1 Treatment compliance

Subjects will receive 1 subcutaneous injection every 4 weeks at 13 visits during the treatment period. Compliance is assured as study drug must/ will be administered by investigator and/or study personnel via subcutaneous injection at the site. Administration of study drug must be recorded in the source documents and the corresponding eCRF for each administration.

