2.7.1.2 Adverse events of special interest / grouping of AEs

Refer to the AEs analyses described in [Section 2.5](#) in this document.

Adverse events of special interest

The following adverse events of special interest (AESI) will be summarized separately by each category and SOC/PT.

Details will be provided in the separate document (eCRS). The search criteria in the latest eCRS corresponding the MedDRA version at the database lock will be used and reported in the CSR.

- Hypersensitivity reactions (including anaphylaxis)
- Cardiovascular and Cerebrovascular (CCV) events
- Neoplastic conditions
- Injection site reactions
- Serum Sickness
- Eosinophilic Conditions / Churg-Strauss Syndrome

- Parasitic (Helminthic) infections
- Thrombocytopenia

Injection site reactions

For injection site reactions (ISR), besides the overall summary table for AESI, ISR will be summarized by events and subject separately in each treatment group for the following categorical variables.

The ISR selected by eCRS as ISR will be mapped to the exposure dosing window. The PTs (possible more than 1 records) happened during the same dosing window (on or after the drug injection administration date and before the next injection administration), they will be considered as one ISR event. If there is any missing dose injection occurred, any selected event will be all considered related to the last drug administration happened. For example, if a dose administration scheduled dose at Week 4 happened, and the next dose administration happened at Week 12 with Week 8 dose administration missing, all injection site reaction happened on or after Week 4 drug administration date before Week 12 drug administration date will be considered related to Week 4 drug administration.

If there were multiple PTs occurred during one dosing window, the worst case will be used for the summary and analysis of ISR. If there is any PT record detailed information (e.g. severity, resolution time, action or outcome etc..) missing or unknown, this PT record will not be included for the particular category summary of ISR. If all PT records for one ISR are with unknown/missing information for the summary category, the ISR will be summarized in the unknown category in the table.

- Recurrence of ISR (single ISR, 2-3 ISRs, > 3 ISRs)
- Severity of ISR (best to worst cases: mild, moderate, severe)
- Timing of ISR (during first administration, Week 4-Week 8, Week 8-Week 24, After Week 24)

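### The injection-site-reaction timing table has unassigned bin boundaries and no per-injection denominator, so its counts rise over time even if the risk per injection is constant

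*SAP*

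**What the plan says.** SAP Section 2.7.1.2 (Injection site reactions) maps each ISR to a dosing window, "on or after the drug injection administration date and before the next injection administration". All preferred terms within one window count as a single ISR. After a missed dose, "any selected event will be all considered related to the last drug administration happened". The SAP's example has Week 4 given, Week 8 missed and Week 12 given, and ties every reaction in between to the Week 4 dose.

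The section continues: "ISR will be summarized by events and subject separately in each treatment group for the following categorical variables". One of those variables is "Timing of ISR (during first administration, Week 4-Week 8, Week 8-Week 24, After Week 24". The SAP gives no rule for the shared boundary, does not say whether timing means onset or attributed dose, and names no denominator of injections given.

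On dosing, Protocol Section 6.6.1 states: "Subjects will receive 1 subcutaneous injection every 4 weeks at 13 visits during the treatment period". Protocol Section 3 puts the first dose on Day 1 and the last on Day 337 (Week 48).

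Three other planned outputs bear on the point:
- a Kaplan-Meier curve for time to first ISR (SAP 2.7.1.2);
- exposure-adjusted incidence rates for adverse events of special interest (SAP 2.7.1.1);
- a per-patient summary of injections given and missed (SAP 2.4.1).

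**The concern.** There are two separate problems. First, the categories are not fully defined. Two programmers could place Week 8 ISRs, Week 24 ISRs and ISRs after a missed dose differently and build different tables from the same data.

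Second, the categories hold very unequal numbers of injections. A table of raw events or subjects will therefore show more ISRs in later categories simply because more injections were given there. A reader looking at when reactions occur over a year of repeated dosing could take that for late clustering. The table alone gives no means of separating a real change in risk per injection from the effect of category width.

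**Working it through.** **Step 1. Number of injections.** First dose Day 1, last dose Day 337, every 28 days: (337 − 1)/28 + 1 = 13. This reproduces the protocol's stated 13. The doses fall at Weeks 0, 4, 8, …, 48.

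**Step 2. Injections per category.** Four allocations are possible, according to where Weeks 8 and 24 are placed:

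| Week 8 goes to | Week 24 goes to | First | Wk 4–8 | Wk 8–24 | After Wk 24 |
|---|---|---|---|---|---|
| later | later | 1 | 1 | 4 | 7 |
| earlier | earlier | 1 | 2 | 4 | 6 |
| later | earlier | 1 | 1 | 5 | 6 |
| earlier | later | 1 | 2 | 3 | 7 |

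**Step 3. Expected share of events.** The documents give no ISR risk per injection, so assume a constant one and full dosing. A category with k injections then has an expected share of k/13:
- First: 1/13 = 7.7%
- Week 4–8: 1/13 to 2/13 = 7.7% to 15.4%
- Week 8–24: 3/13 to 5/13 = 23.1% to 38.5%
- After Week 24: 6/13 to 7/13 = 46.2% to 53.8%

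The last category has 6 to 7 times the events of the first. Because each dosing window yields at most one ISR per subject, the ceilings for 65 fully dosed subjects are 65 × 1 = 65 events in the first category and 65 × 6 = 390 to 65 × 7 = 455 in the last.

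**Step 4. By-subject version.** With risk p per injection, and injections treated as independent, the probability of at least one ISR in a category is 1 − (1 − p)^k.

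| Assumed p | First | Wk 4–8 | Wk 8–24 | After Wk 24 |
|---|---|---|---|---|
| 1% | 1.0% | 1.0–2.0% | 3.0–4.9% | 5.9–6.8% |
| 5% | 5.0% | 5.0–9.8% | 14.3–22.6% | 26.5–30.2% |
| 10% | 10.0% | 10.0–19.0% | 27.1–41.0% | 46.9–52.2% |

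**Step 5. Dropout.** Take the planned 10% and assume it accrues linearly to Week 48, so that injections given at Week w = 65 × (1 − 0.10 × w/48). The dose weeks sum to 312, so the total is 65 × (13 − 0.10 × 312/48) = 65 × 12.35 = 802.75. The first category holds 65/802.75 = 8.1%. After Week 24 it is 359.1/802.75 = 44.7% or 420.9/802.75 = 52.4%. The ratio is still 5.5 to 6.5.

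**Step 6. Onset or attributed dose.** In the SAP's example, an ISR at Week 10 belongs to the Week 4 dose by attribution, hence to Week 4–8. By onset it belongs to Week 8–24. By onset, an ISR between Day 1 and Week 4 that did not occur at the first administration itself has no category. By attributed dose it belongs to the first one.

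**Step 7. Sensitivity to the dose count.** The drug-administration row of Protocol Table 8-1, as extracted, shows 14 marks, and SAP Section 5.1 mentions a Week 52 dosing date. The row may be an extraction artefact; these places should be reconciled with the stated 13. With 14 doses the after-Week-24 share would be 7/14 to 8/14 = 50.0% to 57.1%, so the finding does not depend on this.

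**The case against.** The strongest reply is that the dosing-window rule already settles most of this. Windows run from one injection until just before the next, so Week 4–8 can be read as the window opened at Week 4, and Week 8–24 as those opened at Weeks 8, 12, 16 and 20. That gives 1/1/4/7, a total of 13, with no double count and no gap. This reading is reasonable, but the SAP does not state it for the timing categories. It also puts the Week 24 dose in a category labelled as after Week 24. Even if it is accepted, the last category holds seven times as many injections as the first.

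The second reply is that other outputs cover timing. The Kaplan-Meier curve handles censoring and needs no categories, but shows first ISRs only. The exposure-adjusted rate stops each subject's time at the first episode and is not split by period. The recurrence row counts ISRs without saying when they occurred. The injection summary is per patient, not per category. None supplies a per-injection rate by period for recurrent reactions.

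Three stronger readings are tempting but unsupported:
- **Double counting is certain.** The SAP leaves the boundary open; it does not direct that a Week 8 ISR be counted twice.
- **The table leaves a gap after the first dose.** That holds only on the onset reading.
- **The table bears on dose dependency.** Protocol Section 4.5 says "The exceptions were AEs related to injection site reactions, where a possible trend of dose dependency for ligelizumab was observed", but that concerns dose levels in earlier studies. This trial gives one dose level and cannot address it. The same section describes ISRs as mild to moderate and, apart from one case, non-serious. Nor do the documents say what the timing table is meant to show.

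**Conclusion.** The point holds as an incomplete definition combined with a missing denominator. Week 8 is shared between two categories, Week 24 is not expressly placed, and the basis of timing is unstated. Under every boundary choice, a constant risk per injection puts about 7.7% of ISR events in the first category and 46–54% after Week 24.

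Those shares rest on an assumed constant risk and on 13 doses per subject; 10% linear dropout changes them little. They show what the table would look like with no change in risk. They are not a prediction of the trial's data. A late excess in the table could still be real, but raw counts would not show whether it is.

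The consequence is limited. The table is descriptive, no test is attached to it, and the primary endpoint and the overall ISR incidence, severity, recurrence and outcome summaries are unaffected. This is a minor improvement worth making.

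**What to change.** In SAP Section 2.7.1.2:
1. State that timing follows the dose to which the ISR is attributed under the existing dosing-window rule.
2. Use mutually exclusive categories, for example the Day 1 dose; the Week 4 and 8 doses; the Week 12 to 24 doses; and the Week 28 to 48 doses. These hold 1, 2, 4 and 6 scheduled injections, a total of 13.
3. Beside the counts, report ISRs per 100 injections given in each category, and subjects with an ISR among subjects dosed in that category.

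The per-injection rate is the figure to compare across categories. The by-subject percentage corrects for dropout but still rises with the number of injections per category, as Step 4 shows.

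The cost is a few lines of SAP wording and one denominator. Every administration is already recorded on the eCRF (Protocol Section 6.6.1), so no new data are needed. The change should be made before database lock.

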2.7.1.3 Legal requirements of ClinicalTrials.gov and EudraCT

For the legal requirements of ClinicalTrials.gov and EudraCT, two required tables with treatment emergent adverse events which are not serious adverse events with an incidence greater than 5% and with treatment emergent serious adverse events and SAEs suspected to be related to study treatment, will be provided by system organ class and preferred term on the safety set population. These tables will not be included in the CSR.

If for the same patient, several consecutive TEAEs (irrespective of study treatment causality, seriousness and severity) occurred with the same SOC and PT:

- a single occurrence will be counted if there is ≤ 1 day gap between the end date of the preceding TEAE and the start date of the consecutive TEAE.
- more than one occurrence will be counted if there is > 1 day gap between the end date of the preceding TEAE and the start date of the consecutive TEAE.

For occurrence, the presence of at least one TESAE / TESAE suspected to be related to study treatment / non TESAE has to be checked in a block e.g., among TEAE's in a ≤ 1 day gap block. If at least one SAE is occurring, then one occurrence is calculated for that TESAE.

The number of deaths resulting from TESAEs suspected to be related to study treatment and TESAEs irrespective of study treatment relationship will be provided by SOC and PT.

2.7.2 Deaths

No separate listing or table will be provided from the database. Death will be reported as part of SAE which cause death.

2.7.3 Laboratory data

All laboratory data will be listed by test group, subject, visit and laboratory test with abnormalities flag based on normal ranges. Shift tables for 2 groups of laboratory tests (hematology and serum chemistry) using the low/normal/high classification will be used to compare baseline to the worst on-treatment value. For the parameters with clinically notable abnormal criteria, newly occurred or worsening abnormality will also be summarized. A case is considered as a newly occurring abnormality if the value is not notable or missing at baseline but is notable thereafter during the study. A case is considered as a worsening abnormality if the value is notable at baseline and at least one post-baseline value during the study is worse than baseline.

The laboratory values below Lower Level of Quantification (LLOQ) or above Upper Level of Quantification (ULOQ) will be imputed as LLOQ or ULOQ in the summary tables, respectively. The numerical part of the reported result will be treated as the actual LLOQ or ULOQ. These laboratory values will be displayed in listings using the standard unit with the reported sign (“<” or “>”).

To evaluate potential drug-induced liver injury, newly occurring liver-enzyme abnormalities at any time post-baseline will also be summarized.

The notable criteria and abnormalities are described in section 5.3.

2.7.4 Other safety data

2.7.4.1 ECG and cardiac imaging data

All ECG data will be listed by subject and visit with abnormalities flag based on the notable criteria. A shift table from baseline to the worst post-baseline value will be presented on the overall ECG interpretation. The number of patients with notable abnormal ECG parameters after baseline will be summarized.

The notable criteria and abnormalities are described in section 5.3.

2.7.4.2 Vital signs

All vital signs data will be listed by subject and visit with the abnormalities flag based on the notable criteria. The number of patients with newly occurring or worsening vital sign abnormalities during the study vital signs will be summarized.

The notable criteria and abnormalities are described in section 5.3.

2.7.4.3 Anti-ligelizumab

IG analysis will be performed using the IG analysis set.

The incidence of pre-existing ADAs will be provided, indicating i) the number and percentage of subjects with confirmed positive ADAs at baseline and ii) the number and percentage of subjects with neutralizing ADAs at baseline. The percentage of subjects with neutralizing ADAs is determined based on all subjects with pre-existing ADAs.

Results for ADA (Anti-Drug Antibody) to ligelizumab will be listed by patient, visit/timepoint with the results of the confirmatory assay and the titer values determined. The summary of ADA incidence will be provided for overall population. The listing will also provide annotation with regards to the neutralizing nature of the positive ADA samples. The percentage of subjects with neutralizing ADAs is determined based on all subjects with treatment-emergent ADAs.

Treatment emergent ADAs are defined as ADAs developed on or after the treatment with ligelizumab (Rup et al, 2015, Shankar et al, 2014). Subjects with treatment emergent ADAs may also be sometimes denoted as “ADA-positive subjects”.

[Treatment-emergent ADAs] = [Treatment-induced ADAs] + [Treatment boosted ADAs]

- In a treatment-induced ADA-positive subject, ADAs are developed de novo following biopharmaceutical administration. The pre-dose sample is ADA negative.

- In a treatment-boosted ADA-positive subject, following biopharmaceutical administration a subject with pre-existing antibodies develops an increased level of ADAs which is manifested by a \geq four-fold increase in titer. The pre-dose sample is ADA positive and has a titer.

The ADA incidence summary table will be provided by overall population, indicating i) the number and percentage of subjects with treatment-induced, treatment-boosted and treatment emergent ADAs at anytime and ii) the number and percentage of subjects with neutralizing ADAs at any time, both compared with the total number of subjects in the analysis set who received \geq 1 QGE031 dose.

The following is generated, including all subjects with treatment emergent ADAs: i) a box plot showing the titer distribution per time point, also including for each time point the number of ADA+ samples per total number of ADA samples at that time point (n/m (%)) and ii) the tabulated values of i), e.g. median, Q1, Q3, min, max.

The ADA and neutralizing ADA incidence is determined.

For ADA-positive subjects, provision will be made for a listing of typical immunogenicity-related AEs (generated based on Standardized MedDRA Queries (SMQ) narrow of Hypersensitivity, Anaphylactic reaction, Anaphylactic/anaphylactoid shock conditions and Angioedema, and serum sickness) and the timing of their occurrence along with time course of the occurrence of positive ADAs in those subjects. The safety profile for the ADA positive subjects will be assessed to determine the correlation between occurrence of immunogenicity related AE and ADA positive, i.e., AEs will be summarized in tabular format in the presence or absence of treatment-emergent ADA.

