1.2 Purpose

The effect of ligelizumab in patients with CSU inadequately controlled with H1-antihistamines was investigated in the Phase II dose-range finding study [CQGE031C2201] and demonstrated a dose-dependent response to ligelizumab and superior efficacy in multiple ligelizumab dose groups compared to the omalizumab treatment group. No safety concerns were identified in the ligelizumab groups. Two ongoing Phase III studies, [CQGE031C2302] and [CQGE031C2303], are intended to support the registration of ligelizumab for the treatment of patients with CSU in adolescents and adults inadequately controlled with H1-antihistamines.

There is relatively low number of Japanese subjects treated with the intended dose for registration or higher for 1 year in those Phase III studies above. Therefore, the purpose of this CQGE031C1301 study is to evaluate the safety and efficacy of ligelizumab in adult Japanese subjects with CSU, who remain symptomatic despite treatment with H1-antihistamines at locally-approved doses, over 12 months of treatment with ligelizumab and a post-treatment follow-up period of up to 12 weeks. It is a trial intended to support the registration of ligelizumab for the treatment of CSU in Japan.

2 Objectives and endpoints

[figure not shown]
Table 2-1 Objectives and related endpoints

3 Study design

This is a Phase III multi-center, open-label, single arm study. The study consists of 3 distinct periods:

- Screening period (Day -28 to Day -14): Duration of up to 4 weeks in which subjects who have given informed consent are assessed for eligibility.
- Treatment period (52 weeks): The subjects will be seen in the clinic every 4 weeks.
- Post-treatment follow-up period (12 weeks): This period consists of a subject visit in the clinic every 4 weeks with the final visit (Visit 1999) occurring 16 weeks after the last treatment dose.

Figure 3-1 Study design

Screening period

Subjects will have a screening period to establish eligibility for the study. Subjects will be required to attend 1 visit during screening period: Visit 1 (Day -28 to Day -14). An extended screening period will be permitted only in exceptional circumstances when information concerning eligibility is outstanding (eg, pending laboratory data).

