ePROs should be completed prior to any other assessment and prior to administration of any medication ⁷																			
Dispense Subjects' eDiary	S																		
Collect Subjects' eDiary																	S		
Subjects' eDiary (review compliance) Includes the urticaria patient daily diary (UPDD) [REDACTED]		XS	XS	XS	XS	XS	XS	XS	XS	XS	XS	XS	XS	XS	XS	XS	XS	XS	
DLQI (Dermatology Life Quality Index)		XS	XS	XS	XS			XS							XS	XS	XS	XS	
Laboratory evaluations																			
Stool ova and parasite evaluation ⁸	X																X	X	
Hematology (*INR at Visit1, Visit 110 and UPV)	XS*	XS*	XS	XS	XS	XS	XS*												
Clinical chemistry (**hCG at Visit 1 only) ⁹	XS**	XS	XS	XS	XS	XS	XS	XS	XS	XS	XS	XS	XS	XS	XS	XS	XS	XS	XS
Anti-Drug(ligelizumab) antibodies (ADA)		X															X	X	

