16.5 Appendix 5 [REDACTED] /ADA Log

Period	Visit-Name	Days	Weeks	Anti-Drug-antibodies (ADA)	
				3-x-0.5-mL- serum	Sample- No
Screening	1	-28 to -14	-4 to -2		
Treatment	110	1	0	X	301
	120	29	4		
	130	57	8		
	140	85	12		
	150	113	16		
	160	141	20		
	170	169	24		
	180	197	28		
	190	225	32		
	200	253	36		
	210	281	40		
	220	309	44		
	230	337	48		
	240/EOT/TD	365	52		
Follow-up	310	393	56		
	320	421	60		
	1999/EOS/PSD	449	64	X	302
	UPV			X	3001,- 3002...

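### SAP 2.7.4.3 plans an at-any-time ADA incidence, an ADA time course and an AE-by-ADA correlation, but the only scheduled post-dose ADA sample is at the end-of-study visit

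*SAP*

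**What the plan says.** **Sampling.** The ADA log in Protocol Appendix 5 (Section 16.5) marks three occasions. These are Visit 110 (Day 1, sample 301), the final visit ("1999/EOS/PSD 449 64 X 302") and unplanned visits with open-ended sample numbers. The row for "Anti-Drug(ligelizumab) antibodies (ADA") in Table 8-1 also carries three marks. Protocol Section 3 gives the dosing end, "The last dose of ligelizumab 120 mg will be administered on Day 337 (Week 48, Visit 230) study visit", and places the end of follow-up "with the final visit (Visit 1999) occurring 16 weeks after the last treatment dose".

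**Analysis.** Protocol 12.5.2 asks only for a listing and a count of ADA-positive patients by visit. SAP 2.7.4.3 goes further:

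- an incidence table giving "the number and percentage of subjects with treatment-induced, treatment-boosted and treatment emergent ADAs at anytime";
- a titer box plot by time point;
- for ADA-positive subjects, a listing of immunogenicity-related AEs with "the timing of their occurrence along with time course of the occurrence of positive ADAs in those subjects";
- AE tables split by presence or absence of treatment-emergent ADA, to "determine the correlation between occurrence of immunogenicity related AE and ADA positive".

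**Rules that bear on this.** SAP 2.1.1 keeps unscheduled results out of by-visit summaries and admits them only to maximum or minimum post-treatment summaries. It does not mention ADA status. SAP 2.2 puts a dosed subject in the IG set on the strength of any single immunogenicity assessment. Protocol 6.2.2 says the end-of-study ADA sample is not taken after omalizumab use in follow-up.

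**The concern.** The SAP outputs presuppose repeated ADA measurement during treatment, and the schedule does not provide it. Two consequences follow.

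First, the labels claim more than the data can carry. An at-any-time incidence suggests that ADA was looked for throughout the year of dosing. A time course suggests that antibody onset can be set against the date of an event.

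Second, the only samples beyond the two scheduled ones come from unplanned visits. If those visits cluster in subjects who have events, those subjects get more chances to be classed ADA-positive, and that status is then tabulated against the same events.

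Hypersensitivity reactions including anaphylaxis, and serum sickness, are adverse events of special interest (SAP 2.7.1.2). Evaluating the presence of ADA is a stated purpose of follow-up (Protocol 4.1), and the trial supports Japanese registration (Protocol 1.2). A correlation statement drawn from this sampling could mislead in either direction.

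**Working it through.** The plan states no figure for this point, so there is none to reproduce.

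**1. What is sampled.** Last planned dose Day 337; final visit Day 449.

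- 449 − 337 = 112 days = 16 weeks after the last planned dose.
- 449 − 1 = 448 days after the first dose.
- Post-baseline visits run every 4 weeks from Week 4 to Week 64: 64 / 4 = 16 visits. One of the 16 has an ADA sample.
- Early discontinuers are asked to attend Visits 310 to 1999 (Protocol 9.1.1), so they too are sampled only at their final visit.
- The treatment-emergent AE window closes 16 weeks after the last dose (SAP 2.5.1, 2.5.2), which is when the sample is due.

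**2. What the outputs can show for a subject with no unplanned sample.**

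- At-any-time incidence: one post-dose result, so this is end-of-study incidence.
- Box plot by time point: Day 1 and Week 64 only, if SAP 2.1.1 is applied.
- Time course against AEs: one point, taken after essentially every treatment-emergent AE. Onset, transience and order cannot be determined.

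This step needs no assumption.

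**3. When unplanned samples could distort the AE-by-ADA table.** Suppose ADA and the AE are truly unrelated. Let s be the share of ADA still detectable at Week 64, u the chance of an unplanned ADA sample, and d the chance that this sample catches the ADA. Then

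P(detected | truly ADA-positive) = s + (1 − s) × u × d.

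The documents give none of these. Assume d = 0.8, u = 0.3 to 0.8 with the AE and 0.05 to 0.10 without. Detection ratio, AE to no AE:

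- s = 1: 1.00, whatever u is.
- s = 0.8: 1.04 to 1.15.
- s = 0.5: 1.15 to 1.58. For example, u = 0.5 and 0.05 gives (0.5 + 0.5 × 0.5 × 0.8) / (0.5 + 0.5 × 0.05 × 0.8) = 0.70 / 0.52 = 1.35.
- s = 0.2: 1.48 to 3.07. The upper end is (0.2 + 0.8 × 0.8 × 0.8) / (0.2 + 0.8 × 0.05 × 0.8) = 0.712 / 0.232.

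Equal u in both groups also gives 1.00.

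The SAP tabulates AEs by ADA status, so the ratio has to be turned round. Assume a 15% AE rate and a 5% true ADA rate. At s = 0.2 and u = 0.8 and 0.05, detection is 0.05 × 0.712 = 0.0356 with the AE and 0.05 × 0.232 = 0.0116 without:

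- P(AE | ADA+) = 0.15 × 0.0356 / (0.15 × 0.0356 + 0.85 × 0.0116) = 0.351
- P(AE | ADA−) = 0.15 × 0.9644 / (0.15 × 0.9644 + 0.85 × 0.9884) = 0.147
- apparent risk ratio 2.39, where the truth is 1.

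At s = 0.8 with u = 0.5 and 0.05 it is 1.08.

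**4. If unplanned samples are left out.** Assume AE risks of 45% with ADA and 15% without (true ratio 3), and true ADA rate a. Undetected positives fall among the negatives:

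P(AE | ADA−) = [a(1 − s) × 0.45 + (1 − a) × 0.15] / [a(1 − s) + (1 − a)].

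At a = 0.10, s = 0.2 this is (0.036 + 0.135) / 0.98 = 0.174, and 0.45 / 0.174 = 2.58. Over a = 0.02 to 0.10 and s = 0.2 to 1 the ratio is 2.58 to 3.00. The dilution is mild, but reported incidence falls to s times the true value.

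**5. How much the table can say.** At assumed ADA rates of 1% to 5%, 65 subjects yield 65 × 0.01 = 0.65 to 65 × 0.05 = 3.25 positives. The chance of none is 0.99^65 = 52% to 0.95^65 = 4%.

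**6. Denominator.** Baseline-only subjects are in the IG set and cannot be found positive. As an illustration, if 58 of 65 had a post-dose result, incidence would be scaled by 58 / 65 = 0.89.

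**The case against.** A reader might infer from the schedule that the AE-by-ADA comparison is biased, by a factor of two or three. The documents do not support that. Such a bias needs three things together:

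- unplanned ADA samples taken more often in subjects with these AEs;
- some ADA no longer detectable by Week 64;
- unplanned results counted in ADA status.

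The first is plausible, but the available text does not say what prompts an unplanned ADA sample, and the Table 8-1 footnotes are not in it. The second is unknown. The third is unclear against SAP 2.1.1. If any one fails, unplanned sampling creates no spurious association. A ratio near 3 comes only from the extreme corner of assumed inputs.

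The SAP also already confines the time course to a subject listing. The ADA outputs are descriptive, carry no test and are neither primary nor secondary endpoints, and with so few positives expected the table would be read case by case. Presence of ADA at the end of the study is adequately covered by the schedule.

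All of that stands. It limits the claim about bias but leaves the labelling problem untouched. With few positives, one or two found only at unplanned visits could decide the table.

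A reader might also conclude that ADA status should rest on scheduled samples alone. That would class a subject with a confirmed treatment-emergent ADA at an unplanned visit as negative, against the SAP's own definition, and would lower reported incidence in a safety study.

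**Conclusion.** The concern holds in a limited form. That the at-any-time incidence is an end-of-study incidence for any subject without an unplanned sample, and that onset, transience and temporal order cannot be determined for that subject, follows from the documents without assumption. The AE-by-ADA table is liable to ascertainment bias, probably toward an association, if unplanned samples are event-driven and count toward status. Its size cannot be derived from the documents. On the assumed inputs, the detection ratio runs from 1.0 (ADA persists, or sampling is equal) to about 3.1 (80% of ADA lost by Week 64 and strongly uneven sampling). The denominator is a separate, firmer weakness, because subjects without a post-dose sample can be counted as ADA-negative. The primary and secondary endpoints are not affected. The change is worth making because the SAP promises an incidence and a correlation that the sampling cannot support, and the correction is cheap.

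**What to change.** Amend SAP 2.7.4.3 as follows.

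1. Label the main incidence as treatment-emergent ADA at the scheduled end-of-study sample. Give the any-sample incidence, including unplanned visits, beside it so that no confirmed positive is lost.
2. Present the AE-by-ADA table on scheduled-sample status, with the any-sample version alongside. Flag positives found at unplanned visits, with the reason for the visit.
3. Use as denominator the subjects with a baseline and at least one post-dose ADA result.
4. Keep the ADA time course to the subject listing, and state that transient on-treatment ADA and its temporal order with AEs are not assessed.

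The change is SAP text and programming only, with no new data collection. It costs one extra version of the tables and a smaller denominator.
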